### **2.7.4.2 Vital signs**

Vital signs variables included measurements of oral body temperature, systolic and diastolic blood pressures, pulse and body weight. Vital signs were examined for abnormal values and change from Baseline according to pre-specified clinically notable criteria (see Appendix 2 of study protocol). Appropriate incidence rates of clinically notable abnormalities for between-group differences were provided. Further, descriptive statistics of change from baseline of all vital signs variables were presented by visit. A by-patient listing of all vital signs (with clinically notable abnormalities being flagged) was generated. Shift tables describing changes from baseline based on clinically notable criteria were presented for treatment endpoint (Month 18) and worst on-treatment observations. Only assessments obtained up to 2 days after the discontinuation of study medication were considered “on-treatment”.

## **2.8 Pharmacokinetic endpoints**

Analysis of the Cyclosporin A, Tacrolimus and Everolimus blood levels were done by treatment group and separately for the treatment periods (after Month 6).

### **Everolimus:**

Mean blood level values of Everolimus were presented in tabular form for each timepoint (visit window) and as mean value over time. The number of patients with deviations from the therapeutic window (see section 5.1.4 Target therapeutic ranges) were counted (separately for values “below” and “above” therapeutic range) and tabulated per visit and in total.

Patients with any trough level value outside the therapeutic window were described in detail by narratives reporting also Everolimus dose level and dose adjustments, if applicable.

### **Cyclosporin A:**

Mean blood level values of Cyclosporin A were presented in tabular form for each timepoint and as mean value over time. Blood levels were tried to be kept in therapeutic windows. The number of patients with deviations from the therapeutic window (see section 5.1.4 Target therapeutic ranges) were counted and tabulated per visit and in total.

In the CNI-free group mean blood level values of cyclosporin A were presented in tabular form for each assessment up to Month 8.

### **Tacrolimus:**

Mean blood level values of Tacrolimus were presented in tabular form for each timepoint and as mean value over time. Blood levels were tried to be kept in therapeutic windows. The number of patients with deviations from the therapeutic window (see section 5.1.4 Target therapeutic ranges) were counted and tabulated per visit and in total.

In the CNI-free group mean blood level values of Tacrolimus were presented in tabular form for each assessment up to Month 8.

## **2.9 PD and PK/PD analyses**

Pharmacogenetics/pharmacogenomics were not assessed in this trial.

## **2.10 Patient-reported outcomes**

No health-related Quality of Life assessment was performed in this study.

## **2.11 Biomarkers**

No biomarkers were assessed in this trial.

## **2.12 Other Exploratory analyses**

No additional exploratory analyses were performed.

## **2.13 Interim analysis**

No interim analysis was conducted.

## **3 Sample size calculation**

The probable difference between the CNI-free - and the CNI-group in the GFR was estimated as  $\delta = 8 \text{ ml/min}$  with  $\sigma = 16 \text{ ml/min}$ . With  $\alpha=.05$  (two sided significance level) and  $1-\beta = 90\%$  (power),  $n=86$  patients per group were required to demonstrate superior efficacy of the CNI-free regimen compared to the CNI-group in the GFR using the t-test [REDACTED]. To compensate for some uncertainty of the assumptions for sample size calculation, the calculated sample size was increased by  $\approx 15\%$ . Therefore, a total number of  $N=200$  patients ( $n=100$  per treatment group) were initially planned to be randomized and treated in both treatment arms after Baseline (Month 6 post Tx).

According to amendment 4, enrollment into this study was terminated by 31st December 2015, by that time about 165 patients had been recruited into this trial. Under the assumptions above, this would lead to a power of 82%. Since this sample size also contains patients who discontinued the trial/medication early or who had other protocol deviations, the actual power was even somewhat lower.

## 4 Change to protocol specified analyses

Missing data for the primary outcome variable were dealt with the LOCF method according to protocol, but instead of an additional replacement with the mean of the non-missing values, the LOCF2 method (as described in section 2.5.4) as well as repeated measures analysis (see section 2.5.3) were used.

Not randomized patients were considered for the run-in period but not for the randomized treatment period.

## 5 Appendix

### 5.1 Definitions

#### 5.1.1 Study periods

The following study periods were used for analysis:

- Pre-screening period: Tx – V1/M3/Screening
- Run-in period: V1/M3/Screening – V2/M6/Baseline
- Randomized treatment period: V2/M6/Baseline – V7/M18/EOS
  - Switch period: V2/M6/Baseline – V4/M9
  - Maintenance period: V4/M9 – V7/M18/EOS

In the event of a patient's premature discontinuation, the respective period was defined till the last assessment within this period.

For patients who discontinue prematurely from the study, both, the last available information under study treatment was analyzed.

#### 5.1.2 Calculated GFR

##### MDRD formula

$cGFR$  [ml/min]

$$= 170 \times \text{serum creatinine}[\text{mg/dl}]^{-0.999} \times \text{age}[{\text{years}}]^{-0.176} \times \text{urea nitrogen}[\text{mg/dl}]^{-0.17} \times \text{albumin}[\text{g/dl}]^{0.318} \times C$$

with C=1 for men and C=0.762 for women  
and  $\text{urea nitrogen} = \text{urea}/2.144$

##### Cockcroft-Gault formula

$$cGFR$$
 [ml/min] = 
$$\frac{D \times (140 - \text{age}[{\text{years}}]) \times \text{Body Weight} [\text{kg}]}{72 \times \text{Serum Creatinine} [\text{mg/dl}]}$$

with D=1 for men and D=0.85 for women

*Age*[years]: calculated as (“Visit date” [days] – “Date of birth” [days]) / 365.25

*Age*, *Body Weight* and all serum variables were taken from the respective visit. Missing values of *Body Weight* were imputed by carrying forward the last known observation, if *Body Weight* was missing at Screening (V1/M3), the first non-missing observation was carried backward.

### **5.1.3 Objectives**

#### **Steroids**

- Source: Other Immunosuppressive Therapies
- Occurrence: “Immunosuppressive therapy” WHO ATC codes H02 and L04

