10.4.2 Concomitant therapy

Daily Cyclosporin A and Tacrolimus doses adjusted by the patients' visit-specific body weight, MPA doses, and steroids (expressed in doses equivalent to prednisone) will be summarized by visit and in the same way as the study medication. Data will be presented separately for each treatment group. Induction therapy (Basiliximab or ATG or no induction) received by patient will be summarized by treatment group, for the total (SAF) population, but also for the NRP group.

Duration (days) of treatment with Cyclosporin A, Tacrolimus, MPA, and steroids as well as frequency of Cyclosporin A, Tacrolimus and MPA dose adjustments (including temporary dose interruption) for safety reasons as per protocol guidelines will be determined. Reasons for dose adjustments (including temporary dose interruption) will be presented by frequency distribution. Permanent treatment discontinuations will be analyzed using frequency distribution. All other immunosuppressive therapies will be summarized by ATC (Anatomical, Therapeutic, Chemical) classes.

All analyses for concomitant medication will be presented per treatment group and study phase (see [section 10.1](#)).

Corresponding data of the NRP group will be reported in a similar way.

Medications other than those mentioned in this section taken concomitantly with the study medication will be summarized by treatment group and study period through frequency tables. Concomitant medication will be coded and summarized according to the ATC classification system.

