### **2.1.1 General definitions**

#### Study drug:

The term “Study drug” refers to any drug administered to the patient as part of the required study procedures.

Certican®/ Everolimus was investigational drug. Sandimmun®Optoral/Cyclosporin A, Prograf®/Tacrolimus and MPAs (Myfortic®/EC-MPS or CellCept®/MMF) were considered as study drug as well. Corticosteroids were handled in the same way as concomitant medication.

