## **2.4 Treatments (study treatment, rescue medication, concomitant therapies, compliance)**

### **2.4.1 Study treatment / compliance**

Duration (days) of Everolimus application were summarized. Dose interruptions, i.e. days with dose of 0 mg were considered for calculation of duration. Daily Everolimus dose levels were summarized with mean, standard deviation, minimum, median, and maximum by visit. Dosage averages were calculated including and excluding zero doses for periods of temporary interruption of study medication regardless of whether this was due to safety reasons or patients' non-compliance. Assignment of the DAR records to the visits were calculated based on the visit dates. Reasons for dose adjustments (including temporary dose interruption) were presented by frequency distribution. These frequencies of dose reduction (including temporary dose interruption) for safety reasons as per protocol guidelines were presented by study period. Permanent treatment discontinuations were analyzed by frequencies.

These analyses were performed per treatment group, for the SAF population and related to the study periods in the randomized treatment period (see section 2.1 Data analysis general information). For the run-in period, duration and mean daily dose were summarized for the ENR population displaying both, randomized versus not randomized patients as well as the initial treatment groups CNI+MPA versus CNI+ Everolimus

Daily Cyclosporin A and Tacrolimus doses adjusted by the patients' visit-specific body weight and MPA doses were summarized by visit and in the same way as Everolimus. Data were presented separately for each treatment group. Induction therapy (Basiliximab or ATG or no induction) received by patient was summarized by treatment group, for the SAF population. The distribution of the specific CNI medications was summarized by treatment group.

Duration (days) of treatment with Cyclosporin A, Tacrolimus, MPA, and steroids as well as frequency of Cyclosporin A, Tacrolimus and MPA dose adjustments (including temporary dose interruption) for safety reasons as per protocol guidelines were determined. Reasons for dose adjustments (including temporary dose interruption) were presented by frequency distribution. Permanent treatment discontinuations were analyzed using frequency distribution. All other immunosuppressive therapies were summarized by ATC (Anatomical, Therapeutic, Chemical) classes.

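### The SAP drops the protocol's prednisone-equivalent steroid dose by visit without declaring it, and its ATC rule for identifying steroids is too broad

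*SAP*

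**What the plan says.** Protocol 10.4.2 commits to a dose summary: "steroids (expressed in doses equivalent to prednisone) will be summarized by visit and in the same way as the study medication". It asks for the data separately for each treatment group.

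The matching sentence in SAP 2.4.1 covers the CNI doses adjusted for the patient's "visit-specific body weight and MPA doses were summarized by visit and in the same way as Everolimus". Steroids and the prednisone equivalent are no longer in it. What the SAP keeps for steroids is "Duration (days) of treatment with Cyclosporin A, Tacrolimus, MPA, and steroids", shown per treatment group and study period. It reports the remaining agents apart from these: "All other immunosuppressive therapies were summarized by ATC (Anatomical, Therapeutic, Chemical) classes".

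Two other SAP sections touch steroids. SAP 2.1.1 states: "Corticosteroids were handled in the same way as concomitant medication". SAP 5.1.3 gives an identification rule: "Source: Other Immunosuppressive Therapies", with occurrence defined by "WHO ATC codes H02 and L04".

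SAP section 4 lists two departures from the protocol. One is the replacement of mean imputation for the primary variable. The other is the restriction of non-randomised patients to the run-in period. Neither concerns steroids.

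**The concern.** Steroids are given in both arms according to local standard, and treatment is open-label. Protocol 6.5.2 asks for the dose to stay stable if possible but allows adjustment for medical reasons. A dose-by-visit table by arm is the direct check on whether that happened. Readers of the rejection, infection and laboratory comparisons need it to judge whether the background regimen was alike in the two groups. A duration table cannot stand in for it, because patients at opposite ends of the permitted range contribute the same number of days.

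The one steroid summary that remains may itself be affected. If the rule in SAP 5.1.3 feeds it, and if the second ATC class takes in agents that are not steroids, days on those agents would be counted as days on steroids.

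**Working it through.** The plan gives no figure to reproduce on this point. The check is a comparison of sections, followed by one small calculation.

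**1. Is the dose summary really gone?**

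| Item | Protocol 10.4.2 | SAP |
|---|---|---|
| CsA and tacrolimus dose by visit, weight-adjusted | yes | yes (2.4.1) |
| MPA dose by visit | yes | yes (2.4.1) |
| Steroid dose by visit, prednisone equivalents | yes | absent |
| Steroid duration | yes | yes (2.4.1) |
| Rule for converting to prednisone equivalents | not given | not given |

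Handling corticosteroids as concomitant medication (SAP 2.1.1) does not fill the gap. SAP 2.4.2 gives concomitant medication frequency tables, which carry no dose. Taken literally, it also covers only drugs not mentioned in 2.4.1, and steroids are mentioned there.

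**2. Is the change declared?** No. SAP section 4 lists two changes, and this is not one of them.

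**3. What could a duration table hide?** The inputs are the permitted prednisolone-equivalent ranges.

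- Protocol section 4: 0.05 to 0.3 mg/kg. Ratio 0.3 / 0.05 = 6.
- Protocol 6.5.2: 0.03 to 0.5 mg/kg. Ratio 0.5 / 0.03 = 16.7.
- At an assumed 80 kg, the first is 80 × 0.05 = 4 mg to 80 × 0.3 = 24 mg. The second is 80 × 0.03 = 2.4 mg to 80 × 0.5 = 40 mg.

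These are spans between individual patients who would look identical in a duration table. They do not estimate a difference between arms.

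**4. Does the code rule agree with the rest of the SAP?** SAP 2.4.1 separates steroids from all other immunosuppressive therapies. SAP 5.1.3 assigns two ATC classes to steroids. Assume that H02 is systemic corticosteroids and L04 is the general immunosuppressant class. A non-steroid L04 record from the named source would then belong to both groups, and the two sections conflict.

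Such records are plausible. Protocol Table 6-2 includes anti-lymphocyte antibody therapy for rejection, and protocol 7.1 leaves immunosuppression to the investigator once the protocol regimen has been stopped.

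The size is bounded only loosely. It runs from zero, if the source holds no non-steroid L04 records, up to every such record it holds. The documents do not say how many there are.

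**5. Does it reach the primary analysis?** No. The ANCOVA in SAP 2.5.2 uses treatment, center and baseline GFR, and no steroid variable.

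**The case against.** The strongest reply is that this is a descriptive omission that touches no test, and that the coding complaint rests partly on what the ATC codes contain, which neither document states. Much of that stands.

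- **The codes.** Their meaning is an assumption here, though one the sponsor can check at once against the dictionary that the SAP names.
- **The word joining them.** Elsewhere in the same appendix the SAP writes AND/OR when any listed condition suffices, as for biopsy-proven rejection and myocardial infarction. The steroid line has a plain conjunction. Read as requiring both codes on one record, it would not sweep in every L04 record. Either way the rule needs clarifying.
- **The link to duration.** SAP 5.1.3 gives a source and an occurrence rule. SAP 2.4.1 does not cite it, so the effect on the duration table is inferred.
- **The exposure is narrow.** Everolimus, CNI and MPA are classed as study drugs and summarised on their own, and induction therapy has its own summary. Protocol 6.5.2 does describe a single immunosuppressive therapies form for all such medication, so how far the data source separates these agents should be confirmed.

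A reader might go further and infer that steroid background cannot be compared between the arms at all. The documents do not support this: duration is still presented by treatment group and study period, and other immunosuppressants by ATC class. What is lost is the comparison of dose.

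None of these replies accounts for the missing dose table or for its absence from section 4.

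**Conclusion.** The point holds and is minor. A dose summary that the protocol specifies is missing from the SAP and is not declared. That part rests wholly on the documents. The second part, that the steroid definition is too broad, depends on L04 being the general immunosuppressant class and on the two codes being read as alternatives. The number of records affected is unknown.

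A reader might also conclude that the rejection, infection or laboratory comparisons are confounded, or that investigators gave more steroid after CNI withdrawal. Neither follows. Steroid dose that diverges after randomisation is a co-intervention, possibly a consequence of the assigned regimen. It bears on how a difference is interpreted and does not invalidate the randomised comparison. The protocol sets the same steroid range for both arms in Table 6-1, and nothing in either document shows that doses diverged. The gap is that the planned outputs would not reveal it if they had.

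**What to change.** 1. Restore the protocol 10.4.2 table in SAP 2.4.1: daily steroid dose in prednisone equivalents by visit and treatment group, with the conversion factors stated. If the table is not wanted, declare and justify its omission in SAP section 4.
2. In SAP 5.1.3, restrict steroids to the corticosteroid class (H02), and leave L04 records in the table of other immunosuppressive therapies. State whether this definition feeds the duration summary.
3. Reconcile the two steroid dose ranges, in protocol section 4 and section 6.5.2, which contradict each other.

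The cost is one code list, one descriptive table and a small programming effort for dose conversion. No new data are needed. Protocol 6.5.2 already requires single dose, unit, frequency and dates for all immunosuppressive medication, and protocol 7.4 requires corticosteroid dosages to be recorded throughout the study.

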#### **Treatment failure**

Treatment failure was defined as a composite endpoint of biopsy proven acute rejection of ISHLT 1990 grade  $\geq 3A$  (ISHLT 2004 grade  $\geq 2R$ ), acute rejection episodes associated with hemodynamic compromise, graft loss / re-transplant, death, loss to follow up (at least one condition must be present).

#### Biopsy proven acute rejection

- Source : Endomyocardial biopsy CRF at respective visit
- Occurrence: “ISHLT grade / 1990” in (“Grade 3A”, “Grade 3B”, “Grade 4”) AND/OR “ISHLT grade / 2004” in (“Grade 2R moderate”, “Grade 3R severe”)
- Date of event: “Date of biopsy”

#### Acute rejection episodes associated with hemodynamic compromise

- Source: Endomyocardial biopsy CRF at respective visit
- Occurrence: “Is hemodynamic compromise present?” = 1 (“Yes”)
- Date of event: “Date of biopsy”

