Fractional shortening \leq 20% or 25% lower than baseline and/or Inotrope treatment
Baseline is defined as Visit 1

Treatment of CMV

Treatment with gancyclovir, cytomegalovirus hyperimmune globulin, valgancyclovir or valacyclovir is permitted and will be at the investigator's discretion per standard practice of the individual centers. Non-high risk patients will be treated according to local practice. CMV prophylaxis is also recommended following any antibody treatment of acute rejection episodes.

Treatment of *Pneumocystis carinii*

All patients should receive prophylactic treatment for *Pneumocystis carinii* Pneumonia (PcP) with trimethoprim/sulfamethoxazole (e.g. Bactrim[®] or Cotrim[®]) according to local practice. Duration and dosage depend on the discretion of the investigator. Aerosolized pentamidine or dapsone may be administered to patients unable to tolerate oral formulations.

Treatment of Candida

Nystatin for oral thrush (Candida) will be used in a swish and swallow regimen. Routine use of systemic antifungal agents (i.e., ketoconazole, itraconazole, and fluconazole) will not be allowed unless patients are systemically infected. Administration of azoles may increase blood concentrations of Cyclosporin A, Tacrolimus and Everolimus; therefore their use should be minimized. Particular attention to side effects is required. If such agents are to be used, additional drug monitoring Cyclosporin A, Tacrolimus and Everolimus are recommended at start and end of treatment.

Treatment of hyperlipidemia

Lipid lowering medications (e.g. fluvastatin, Lescol[®]) are to be administered to all patients even if the patient does not have an elevated LDL-cholesterol or triglyceride levels at baseline. Initiation of treatment should follow the National Cholesterol Educating Program (NCEP) guidelines (Appendix 6).

The daily starting dose should be the equivalent of 20 mg pravastatin, 5 mg simvastatin, 10 mg atorvastatin, or 20 mg fluvastatin, and may be increased to target and maintain a LDL level of < 130 mg/dL. In case of simvastatin, dose should not exceed 10 mg/day to account for the increased risk of myopathy/rhabdomyolysis, when combined with Cyclosporin A.

When HMG-CoA reductase inhibitors are used concomitantly with gemfibrozil (and probably other fibrates), Cyclosporin A or erythromycin, myopathy and rhabdomyolysis have been reported. **Therefore, the use of lovastatin will be prohibited in this study.**

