7.5 Efficacy

The following efficacy variables will be obtained and recorded:

- **Endomyocardial biopsy – Rejection episodes / graft loss / re-transplant**

Per protocol biopsies will be performed at visits 2, 4, 6 and 7 and results of a biopsy that may have been performed at Month 1 post Tx will be recorded retrospectively. Additionally, a biopsy will be performed in any case of suspected rejection. Biopsies will be read and interpreted by local pathologists according to the ISHLT 1990 and/or 2004 diagnosis criteria ([Stewart et al, 2005](#)). A copy of the pathology report will be collected and filed in the investigator's folder. The results will be recorded on the Endomyocardial Biopsy CRF at respective visit.

All suspected rejection episodes must be recorded on the Endomyocardial Biopsy log / Suspected Rejection CRF, with the date rejection was first suspected, whether anti-rejection therapy was administered, whether the acute rejection was confirmed or with final clinical diagnosis specified, and final clinical outcome.

Biopsy-proven acute rejection

(ISHLT 1990 grade \geq 3A resp. ISHLT 2004 grade \geq 2R)

The occurrence of a biopsy-proven acute rejection is diagnosed from per-protocol biopsies or from biopsies performed for suspected rejection episodes. Per protocol biopsies will be performed at Visits 2, 4, 6 and 7 / 7.1.

In all suspected rejection episodes, a graft core biopsy and an echocardiography will be performed within 48 hours, regardless of the initiation of anti-rejection therapy. The results including date of occurrence of first symptoms will be recorded in the Endomyocardial Biopsy log / Suspected Rejection CRF and will be used for the efficacy analysis.

Rejection episodes will be reported on the Endomyocardial Biopsy log / Suspected Rejection CRF only, and not on the AE CRF. An Endomyocardial Biopsy log / Suspected Rejection CRF will be completed each time a suspected or biopsy-proven acute rejection has occurred. Rejection episodes occurring more than 10 days after the start of the preceding one will be considered as a new rejection episode.

Rejection with hemodynamic compromise

The occurrence of an acute rejection with hemodynamic compromise will be assessed using the Hemodynamic Compromise CRF. Positive inotrope therapy or vasoactive treatment will be recorded on the Prior-/Concomitant medications CRF.

Graft loss / re-transplantation

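### The SAP rule for acute rejection with hemodynamic compromise tests only for compromise, states no rejection condition, and uses a different form from the protocol

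*SAP*

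**What the plan says.** Protocol section 3 and SAP sections 1.2, 2.6.1 and 5.1.3 define treatment failure as a composite. One component is "acute rejection episodes associated with hemodynamic compromise".

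SAP section 5.1.3 then gives a derivation for each component. For this one:

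- Data source: "Source: Endomyocardial biopsy CRF at respective visit".
- Occurrence: "Is hemodynamic compromise present?” = 1 (“Yes".
- Event date: the date of the biopsy.

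The rule just above it, for biopsy-proven acute rejection, uses the same form and does state grades, for example "ISHLT grade / 2004” in (“Grade 2R moderate”, “Grade 3R severe" for the 2004 classification.

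Protocol 7.5 names another source for the compromise component: "The occurrence of an acute rejection with hemodynamic compromise will be assessed using the Hemodynamic Compromise CRF". Suspected rejections go on the Endomyocardial Biopsy log / Suspected Rejection CRF, which records "whether the acute rejection was confirmed or with final clinical diagnosis specified".

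Under SAP section 2.6.2 the composite and each component are analysed by Kaplan-Meier and log-rank test. Section 2.6.1 calls these variables exploratory.

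**The concern.** The component needs two things together, a rejection and compromise. The Occurrence line tests only the second. A programmer who follows it would score a patient with compromise on a biopsy form as a rejection failure even if the biopsy showed no rejection and the clinical diagnosis was something else.

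The study expects better renal function without CNI and comparable efficacy. Treatment failure is where the efficacy half of that expectation is examined. Non-rejection events spread evenly over the arms would make the arms look more alike, which is the result the study expects. Uneven recording, which is possible in an open-label trial, could push the comparison either way.

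**Working it through.** No figure in either document depends on this rule, so there is nothing to reproduce. The check is a comparison of texts, followed by an illustration of direction only.

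**1. Does the tick imply rejection?** The footnote to protocol Table 6-2 defines compromise by ejection fraction, by fractional shortening (a fixed limit or "25% lower than baseline and/or Inotrope treatment"), or by inotropes. No rejection criterion appears. Protocol Table 7-1 gives rejection episodes and hemodynamic compromise separate rows, and the visit procedures and SAP section 2.1 list them as separate items. The documents therefore treat the two as distinct.

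**2. Can the tick sit beside a biopsy without rejection?** Protocol 7.5 states: "Per protocol biopsies will be performed at visits 2, 4, 6 and 7". Visits 4, 6 and 7 (Months 9, 12 and 18) follow randomization, and these biopsies do not depend on suspicion. From Month 6 on, the visit procedures ask for information on compromise at every visit. The protocol also foresees suspected rejections that are not confirmed, because the log has a field for that. Neither document rules the combination out.

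**3. Does another line of the SAP supply the condition?** The heading of the rule names acute rejection, so the intent is clear, but the Occurrence line does not carry it. The neighbouring rule shows that the SAP writes a grade condition out where it wants one.

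**4. Which events does this component add to the composite?** A biopsy graded 3A or higher (1990), or 2R or higher (2004), already counts as biopsy-proven rejection. A biopsy that enters the composite only through the compromise item therefore has a lower grade. For those events the tick is the whole evidence, and the SAP checks nothing else.

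**5. Source.** The protocol sends this component to the Hemodynamic Compromise CRF. The SAP uses the biopsy form of the visit. SAP section 4 lists changes to missing-data handling and to non-randomized patients, but not this one. Read literally, the SAP source could also miss episodes documented between visits on the log.

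**6. Direction, with assumed rates.** Let p be the true failure rate in an arm, and q the rate of compromise without rejection, equal in both arms and independent of true failure. The observed rate is p + (1 − p)q, so the difference between arms becomes (p₂ − p₁)(1 − q). None of these rates comes from the documents.

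| Assumed true rates | q | Observed rates | Risk ratio |
|---|---|---|---|
| 10% and 20% | 0 | 10.0% and 20.0% | 2.00 |
| | 2% | 11.8% and 21.6% | 1.83 |
| | 5% | 14.5% and 24.0% | 1.66 |
| | 10% | 19.0% and 28.0% | 1.47 |
| 5% and 15% | 0 | 5.0% and 15.0% | 3.00 |
| | 5% | 9.75% and 19.25% | 1.97 |
| | 10% | 14.5% and 23.5% | 1.62 |

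Worked line: 0.10 + 0.90 × 0.05 = 0.145; 0.20 + 0.80 × 0.05 = 0.240; 0.240 / 0.145 = 1.66. Equal misclassification pulls the ratio towards 1. The table does not estimate what happened in this trial.

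**The case against.** The strongest objection is that the case report form is not among the documents. The item may be asked only after a rejection question has been answered yes, in which case the condition is already in the data. Two features of the text point that way: the rule's heading, and Table 6-2, which crosses compromise with grades 1A to 4 and has no row for grade 0. This objection stands in part. It limits what can be said about the effect, but a derivation that relies on the layout of a form should say so.

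Second, echocardiograms are not scheduled. Table 7-1 and protocol 7.5 have them done as needed, for suspected rejection. At a routine biopsy the ejection-fraction and shortening criteria may have no measurement behind them, leaving mainly inotrope use or an echocardiogram done for another reason. This makes the routine-biopsy route less likely, but not impossible.

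Third, the endpoint is exploratory. Treatment failure has no margin or formal non-inferiority test, and the SAP's heading for a key secondary analysis is empty. This stands, and it limits the weight of the point.

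A reader might infer more: that false rejection events were in fact counted, or that compromise from any cause counts. The documents support neither. The first depends on the unseen form, and the second is too wide because compromise with no biopsy form is not captured. Nor can patient numbers be put on it. Any per-biopsy rate would be invented, repeated biopsies in one patient are not independent, and patients who have already failed on another component add nothing to the composite.

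**Conclusion.** The point holds as a defect in the written rule. The component is defined as rejection with compromise, and the derivation tests compromise alone. As written, compromise recorded on a biopsy form without rejection would count in the exploratory composite and in its own log-rank comparison. The source form also departs from protocol 7.5 without being listed as a change.

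The size is unknown. It is zero if the item is nested under a rejection question, and otherwise it depends on a rate that neither document gives. If the extra events fall equally on both arms, they draw the arms together. The primary GFR analysis is not affected. The correction is worth making because it is short and uses information the protocol says is recorded.

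**What to change.** Rewrite the Occurrence line in SAP section 5.1.3 to require compromise = Yes **and** an acute rejection for the same episode. The rejection can be shown in either of two ways:

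- the Endomyocardial Biopsy log / Suspected Rejection CRF records it as confirmed, or gives rejection, including antibody-mediated rejection, as the final clinical diagnosis; or
- that biopsy carries a qualifying rejection grade.

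Take the qualifying grade from the protocol's own rejection definitions and fix it before database lock. The choice matters. Table 6-2 considers compromise from grade 1A (1R) upward, while biopsy-proven rejection starts at 3A (2R). At the higher limit the grade route adds nothing to the composite beyond biopsy-proven rejection. A grade rule alone would also miss antibody-mediated rejection, which protocol Appendix 7 records separately from the cellular grade.

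In the same edit, reconcile the source form with protocol 7.5, say how records of one episode are matched across forms, and enter any change in SAP section 4. If the form already nests the item under a rejection question, state that. List Yes answers without rejection separately by arm.

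The SAP's document history places this version before database lock. If the data have since been analysed, run the conditioned definition as a sensitivity analysis and report how many events drop out.

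The cost is a short change to one derivation plus matching across forms, for which the documents name the fields but no linking key. The downside is that an episode with a negative biopsy counts only if it was confirmed clinically.
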